Aims: To collect pilot data to establish the feasibility of a randomized controlled trial (RCT) of a manualized Compassion Meditation (CM) group treatment to restore functioning in older Veterans with psychological distress. Key questions include:

- (1) Will older Veterans with anxiety and/or depression enroll in and complete the proposed CM intervention?
- (2) What is the completion rate?
- (3) Do participants adhere to the treatment (complete practice at home)?
- (4) Are modifications required for the intervention to make it more acceptable and appropriate for older Veterans with emotional distress (e.g., length of session, pace of material, mechanism for supporting home

practice)?

(5) Does CM show promise for improving well-being, symptom severity, and/or positive psychological factors relevant to successful aging?

We also seek to optimize the assessment strategy for a future Merit Award application, including to explore feasibility of inflammatory biomarkers as a CM intervention outcome.

Section 7 - Background and Significance

7) Provide a succinct discussion of relevant background information to justify performing the proposed study.

Critical unmet need: Over the past decade, there has been unprecedented growth in the number of older Veterans who are at elevated risk for clinically significant emotional distress, but are less likely than younger Veterans to utilize specialty mental health VA clinics. These mental health concerns can result in considerable disability, medical comorbidity, higher health care utilization and costs, reduced physical and mental well-being, and higher mortality). The VA's Primary Care – Mental Health Integration (PCMHI) services are an important component in addressing such concerns, but older age remains associated with low mental health service utilization among psychologically distressed Veterans (Blais et al., 2015). If compassion-based interventions can be effectively tailored such that the benefits generalize to older

Veterans, then there is a unique opportunity for an evidence-based, novel treatment that not only reduces psychological distress, morbidity and mortality, but also promotes "healthy aging" and increases well-being (Jeste et al., 2015).

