CM intervention: Through the experience and feedback from the three successful CM groups we will adapt the CBCT-Vet([name] et al., 2017) intervention for use in older adults with anxiety or depressive symptoms. This adaptation will be conducted with input from [name] and [name] (developers of CBCT® and consultants for the proposed project), and the experience and expertise of the study team. Expected adaptations include changing the focus of examples from PTSD to anxiety and depression, as well as adjustments for appropriate use with older Veterans. The CBCT-Vet includes 10 90-minute sessions that will be led by [name], a VA Staff Psychologist and Co-Investigator on the proposed project, who is certified in CBCT® with significant experience in administering CBCT-Vet. Sessions 1 - 4 assist participants in basic mindfulness breathing practices; sessions 4 - 8 focus on personal analysis of factors underlying difficulties with compassion for self or others; the final two sessions (9 and 10) review content and assist with relapse prevention. Session by session topics are: (1) Introduction and learning breathing meditation, (2) Focused attention, (3) Creating space, (4) Mindful awareness, (5) Re-engaging with heroic spirit, (6) Seeing ourselves in others, (7) Appreciation and gratitude, (8) Empathy and engaged compassion, (9) "Putting it all together," and (10) "Putting it all together 2."

Our target is to have 5-8 participants completing each 10-week intervention, thus we will enroll up to 10 per group to account for possible attrition. Two or three of the CBCT-Vet groups (depending on the degree of modification needed based on the initial group) will be conducted sequentially, such that information in the first group can be used to adapt the manualized intervention for the next group.

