Descriptive statistics will be used to summarize the variables as well as to detect outliers and data entry errors. When applicable, normality of the distribution will be examined for outcome variables and residuals of regression model with a normal probability plot. The present project is intended as a feasibility study that will inform, support, and guide development of a subsequent larger-scale VA Merit Award project. Therefore, the primary analysis will be descriptive rather than hypothesis testing. Since the interventions are delivered by group (8-10 participants per group), it is possible that measured or unmeasured characteristics of the participants in a given group or their interactions may affect psychological response to the intervention, attendance, and study outcomes. The analysis plan described below is based on no cluster effect of class. But we will assess the impact of clustering effects by fitting a random effects model for each outcome, and, if necessary, a random class effect will be included in the model to account for the correlations between the individuals in the same class. The intraclass correlation coefficient (ICC) will also be estimated to understand the correlation within class and provide advice for sample size adjustment in future studies.

Will older Veterans with psychological distress [anxiety and/or depression] enroll in and complete the proposed CM intervention? What is the completion rate? Do participants adhere to the treatment (complete practice at home)? We will assess the following outcome measures for enrollment, completion, and adherence to treatment:

- 1) $\underline{\it Enrollment\ rate}$ defined as the proportion of consented subjects among all screened and eligible patients;
- 2) Initiation rate defined as the proportion of subjects who initiate the intervention among all consented subjects;
- 3) $\underline{Completion\ rate}$ defined as the proportion of subjects who complete 6 or more sessions (out of a total of 10 sessions) of intervention among those who start the intervention;
- 4) Practice time at home defined as average minutes that subjects practice at home each week. The mean (and SD) or percentage will be calculated and the 95% confidence intervals will be estimated for all outcomes.

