The sample size justification was conducted for assessing the enrollment and completion rates (primary outcomes). We assessed the precision of estimates based on projected sample size. From previous investigations, the estimated enrollment and completion rates are between 0.57 and 0.82. Therefore, we considered a range of rate from 0.60 to 0.90 and estimated the margin of error (half of the width) for the 95% confidence interval of enrollment and completion rates. The margin of error of a 95% confidence interval for a proportion is 1.96*p*(1-p)/(Square-root of n) where n is the estimated sample and p is the estimated rate. If an estimated intervention initiation rate is 0.80, a sample size of 30, 27 and 24 will produce a two-sided 95% confidence interval with a margin of error of 0.058, 0.071 and 0.064, respectively. For an estimated completion rate of 0.60, a sample size of 30, 27 and 24 will produce a two-sided 95% confidence interval with a margin of error of 0.086, 0.091 and 0.096, respectively.

We assessed the power for detecting a significant change in psychological outcomes. With a sample size of 24, 27 and 30, we will have 80% power to detect an effect size of 0.53, 0.56 and 0.60 for the change in outcomes from baseline to post-intervention. These effect sizes are achievable based on previous studies, where we observed an effect size of 0.5 for PHQ-9 (mean = 2.3, SD = 4.6), 0.65 for SCS-R (mean = 6.4, SD = 9.9), 1.4 for SWLS (mean = 9.0, SD = 6.6), 0.53 for mDES positive emotion (mean = 4.8, SD = 9.1), and 5.35 for mDES negative emotions (mean = 7.5, SD = 1.4).

Women and ethnic minorities: Women and ethnic minorities will be included in proportion to their representation of Veterans in the VASDHS and PCMHI program. This proportional sampling plan fosters both feasibility of the study and overall generalizability of findings. We recognize that the issues of anxiety and depression among women Veterans is exceptionally important, but warrants separate studies designed and focused specifically to address the issues of most salience to women Veterans.

Children: No children will be included as the scientific focus of this project is on older Veterans

Temporary COVID-19 Updates*

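### Completion is defined only among Veterans who start CM, while key question 1, the class-size target and the completion precision all work per enrolled Veteran; a completion rate among all consented, with its own interval, should be pre-specified

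*Combined protocol and SAP*

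**What the plan says.** All of this is in the combined protocol and SAP.

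- **Section 6, key question 1**, repeated in the Section 9 Analytic plan in nearly the same words, asks: "Will older Veterans with anxiety and/or depression enroll in and complete the proposed CM intervention". Key question 2 asks separately for the completion rate.
- **Section 9, Analytic plan**, lists three rates in sequence. Enrollment is "defined as the proportion of consented subjects among all screened and eligible patients". Initiation is "defined as the proportion of subjects who initiate the intervention among all consented subjects". Completion is the proportion attending at least 6 of the 10 sessions "of intervention among those who start the intervention". Each is to be reported with a 95% CI.
- **Section 9, Sample size assessment**, names two of the three as primary: "The sample size justification was conducted for assessing the enrollment and completion rates (primary outcomes"). It plans 24 to 30 Veterans for the CM groups and gives the completion precision at n = 30, 27 and 24.
- **Section 9, CM intervention**, sets the class size: "Our target is to have 5-8 participants completing each 10-week intervention, thus we will enroll up to 10 per group to account for possible attrition".

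**The concern.** The two named primary outcomes do not join up. The first ends at consent and the second begins at the first session attended. A Veteran lost between those points is a success in one and is missing from the other, so neither primary outcome records that Veteran as a failure. Such loss is plausible, because consent is taken at a Baseline Visit before the classes, and the classes run one after another.

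Two other parts of Section 9 work per enrolled Veteran. The class-size target compares completers with Veterans enrolled, and the completion precision uses the planned enrollment as its n. The study exists to inform a larger trial, and that trial will fill its class places with consented Veterans. A planner who takes the completion rate as a per-enrollee figure would expect more completers per class than the data support.

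**Working it through.** **Inputs.** From the Sample size assessment: completion 0.60; initiation 0.80, introduced conditionally ("If an estimated intervention initiation rate is 0.80"); n = 30, 27, 24; printed margin formula 1.96·p·(1−p)/√n. From the CM intervention text: up to 10 enrolled and 5 to 8 completing per group. The other initiation rates below are assumptions, used to show the range.

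**Step 1: reproduce the plan's completion precision, to see which n it uses.** With p = 0.60, p(1−p) = 0.24.

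- n = 30: 1.96 × 0.24 / √30 = 0.086
- n = 27: 1.96 × 0.24 / √27 = 0.091
- n = 24: 1.96 × 0.24 / √24 = 0.096

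These match the printed 0.086, 0.091 and 0.096. The completion precision is therefore computed on the full planned CM enrollment, although the Analytic plan's denominator is starters. If 0.80 start, the starters number 0.80 × 30 = 24, 0.80 × 27 = 21.6 and 0.80 × 24 = 19.2.

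The printed formula lacks the square root over p(1−p). That is a separate matter, but it affects any margin quoted here. With the usual 1.96·√(p(1−p)/n):

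| Planned CM enrollment | p = 0.60, n = all enrolled | p = 0.60, n = starters (0.80 start) | p = 0.48, n = all consented |
|---|---|---|---|
| 30 | 0.175 | 0.196 | 0.179 |
| 27 | 0.185 | 0.207 | 0.188 |
| 24 | 0.196 | 0.219 | 0.200 |

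**Step 2: the gap between the two denominators.** Let i be the initiation rate and c the completion rate among starters. Completion among consented = i × c. The relative excess of the starters' rate = c/(i × c) − 1 = 1/i − 1, so c cancels and only initiation matters. With c = 0.60:

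| Initiation i | Completion among consented (0.60 × i) | Relative excess (1/i − 1) | Expected completers per 10 enrolled |
|---|---|---|---|
| 1.00 | 0.60 | 0% | 6.0 |
| 0.90 | 0.54 | 11% | 5.4 |
| 0.80 | 0.48 | 25% | 4.8 |
| 0.70 | 0.42 | 43% | 4.2 |

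At 0.80 the difference is 0.60 − 0.48 = 0.12. The expected 4.8 completers per 10 enrolled falls just below the 5-to-8 target, where 6.0 falls inside it.

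**Step 3: what the report would show.** Take an invented result with 30 consented to CM, 24 starting and 14 completing. Among starters, 14/24 = 0.58 (exact 95% CI 0.37 to 0.78). Among consented, 14/30 = 0.47 (0.28 to 0.66). The plan as written yields the first estimate and interval, and an initiation rate of 24/30 = 0.80 with its own interval. Multiplying the two point estimates recovers 0.47, but the interval for 0.47 has to be computed from the counts, and nothing in the plan says it will be.

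**The case against.** The case for leaving the plan alone is substantial.

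- **Non-starters are already counted.** Initiation sits between enrollment and completion, under the same question, with a 95% CI. The three rates form a chain, and the counts behind them give completion among consented directly. This stands. A reader might infer that non-starters vanish from the plan or that key question 1 goes unanswered; the listed outcomes taken together do not support that.
- **The starters' rate is not biased.** It estimates what its definition says. A reader might infer that the plan overstates completion by 25%. That holds only if the rate is read as an enrollee rate, which the definition does not invite.
- **The 0.80 is insecure.** It is a conditional example. The quoted prior range, 0.57 to 0.82, is for enrollment and completion, and the word initiation may be a slip for enrollment. In that case the plan offers no initiation figure at all. Also, 0.60 is applied to the full enrollment; if it was meant per enrolled Veteran, multiplying it by 0.80 counts the loss twice and 10 enrolled would give 6.0 completers. All of this stands, and is why the size is given as a range.
- **The class target can be checked without any rate.** Completers per class can simply be counted. This stands: it would be wrong to say that the starters' definition prevents that check.
- **No decision threshold hangs on completion**, and the primary analysis is descriptive. This stands and limits the importance of the point.

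What remains unanswered is that initiation is not named primary, that no interval is planned for completion among all consented, and that Section 9 uses two denominators for completion.

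**Conclusion.** The point holds as a mismatch of denominators and a missing pre-specified estimate. It is not an error in the starters' rate. The excess of the starters' rate over the consented-based rate is 1/i − 1: zero if all start, 11% at 0.90, 25% at 0.80 and 43% at 0.70. Only the 0.80 appears in the plan, as an illustration. The absolute figures (0.60 against 0.48) further assume that 0.60 refers to starters, as the Analytic plan defines it. The inconsistency in n between the Analytic plan and the Sample size assessment does not depend on any of these rates. This is a cheap improvement to a descriptive feasibility study.

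**What to change.** In the Section 9 Analytic plan, pre-specify completion as the number attending 6 or more of the 10 sessions divided by all consented Veterans assigned to CM, counting non-starters as non-completers, with a 95% CI. State that this rate answers key question 1 and is the one to use when planning class sizes. Restrict the denominator to CM, since the healthy aging group also consents participants. Keep completion among starters and the initiation rate beside it, because together they show where the losses occur.

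In the Sample size assessment, make the n for completion match the chosen denominator: 24 to 30 if it is all consented, or the expected number of starters if the starters' rate is retained there. State also which denominator the 0.60 and the prior completion rates refer to, and confirm whether the 0.80 is meant for initiation.

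The cost is a few sentences and one more proportion from data already collected. The downside is that the headline completion figure may be lower than the starters' rate.

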The associations between patient characteristics and other clinically important baseline variables with the enrollment, completion and adherence will be assessed using univariate tests (Wilcoxon rank sum test, Kruskal-Wallis test, Fisher's exact test, or Spearman correlation coefficient).

Does CM show promise for improving well-being, symptom severity, and/or positive psychological factors relevant to successful aging? We will evaluate the improvement in depression and anxiety (BSI), social connection (SCS-R), satisfaction with life (SWLS) and positive emotions (mDES) from baseline to post-intervention using a linear random effect model and time will be included as a main effect in the model. The random effects model is suitable for examining changes in outcomes in longitudinal studies. It will include all available data, minimizing the effects of missing data on the analyses.

We will also examine the mean (and SD) change scores for each inflammatory biomarker (hs-CRP, IL-6, and TNF-), as well as the association of these changes with practice time.

Sample size assessment:

The sample size was determined based on practical consideration. Since this is a feasibility study, the goal is to examine the effect size such that it can guide future studies. We plan to enroll a total of approximately 24 to 30 participants for the CM groups (3 groups, 8-10 per group) as well as 10 participants for the healthy aging group. Sample size analyses were focused on the CM group, and performed using statistical package R.

A two-sided type I error of 0.05 was assumed.

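### The plan names no interval method for its feasibility rates, and the only one it shows, the symmetric normal-approximation margin, covers about 91–92% on average at the planned sizes even when correctly written

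*Combined protocol and SAP*

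**What the plan says.** Section 9, Analytic plan, defines enrollment, initiation and completion rates and practice time at home. It then says: "The mean (and SD) or percentage will be calculated and the 95% confidence intervals will be estimated for all outcomes". No interval method for a proportion is named there.

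Under Sample size assessment in the same section, enrollment and completion are called the primary outcomes, and the planned precision is worked out. The inputs are earlier experience ("the estimated enrollment and completion rates are between 0.57 and 0.82"), a planning range ("we considered a range of rate from 0.60 to 0.90") and a CM sample of 24 to 30. The formula reads: "The margin of error of a 95% confidence interval for a proportion is 1.96*p*(1-p)/(Square-root of n". It is the only interval expression for a rate in the document. No score, exact or other small-sample interval appears.

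The Analytic plan takes no class effect as its base case. A class term is added to a random effects model only if needed, and it is not described as a way of forming intervals for the rates.

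**The concern.** This is a feasibility study with a descriptive primary analysis, so the rates and their intervals are the main result. The lower limit matters most, because it shows how low initiation or completion could plausibly be when the larger trial is planned.

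A symmetric normal-approximation (Wald) interval is known to cover too little when the sample is small and the rate is well above one half. If the analyst carries the planning formula into the report, even after repairing it, the intervals labelled 95% will fall short, mostly by setting the lower limit too high. Observed rates close to 1 would also give limits above 100% or an interval of zero width. Such rates are plausible: completion needs only 6 of 10 sessions among those who start, and entrants must state that they intend to attend.

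**Working it through.** **Inputs from the plan.** n = 24, 27 and 30; planning range 0.60–0.90; earlier estimates 0.57–0.82; two-sided 5% level.

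**1. The plan's own margins.** The printed formula, 1.96·p(1−p)/√n, gives the following for n = 30, 27, 24:
- Rate 0.80: 0.0573, 0.0604, 0.0640. The plan states "margin of error of 0.058, 0.071 and 0.064, respectively".
- Rate 0.60: 0.0859, 0.0905, 0.0960. The plan states 0.086, 0.091, 0.096.

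Four of the six agree to rounding, 0.058 is off by about 0.001, and 0.071 does not reproduce. The correct Wald margin is 1.96·√(p(1−p)/n). At rate 0.80 and n = 30 this is 1.96·√(0.16/30) = 0.143. The full sets are 0.143, 0.151, 0.160 at rate 0.80 and 0.175, 0.185, 0.196 at rate 0.60. The missing square root is a separate error. Everything below uses the correct Wald form.

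**2. Exact coverage of the correct Wald interval.** For true rate p, coverage is the sum of the binomial probabilities P(X = x) over every x whose interval contains p.

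| True rate | n = 30 | n = 27 | n = 24 |
|---|---|---|---|
| 0.60 | 93.5% | 92.4% | 93.8% |
| 0.80 | 94.6% | 91.7% | 87.3% |
| 0.90 | 80.9% | 93.8% | 91.3% |

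Example, n = 30 and p = 0.90. The interval misses from above at 29/30 (lower limit 0.902) and at 30/30 (a point at 1): 0.1413 + 0.0424 = 0.1837. It misses from below at 22 or fewer: 0.0078. Coverage is 1 − 0.1837 − 0.0078 = 0.8085.

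**3. Over a grid of rates in steps of 0.001, n = 24 to 30.**
- Rates 0.60–0.90: mean coverage 91.4–91.8%. The minimum for each n is 79.9–80.9%, at rates of about 0.88–0.90. At n = 24, 27 and 30, coverage is below 90% over 19–23% of the range and below 85% over 3–5%.
- Rates 0.57–0.82: mean about 92–93%, minimum about 86–89% depending on n.
- Direction, over 0.60–0.90: the lower limit lies above the true rate about 6.5–7% of the time, against a nominal 2.5%. The upper limit lies below it about 1.7% of the time.
- Wilson, over 0.60–0.90: mean 95.2–95.3%, minimum 92.1%. Clopper-Pearson: never below 95%.

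**4. Behaviour near 1.** The Wald upper limit passes 1 from 27/30, 24/27 or 21/24 upward, and the width is zero when everyone succeeds. At 27/30, Wald gives 0.79–1.01 and Wilson 0.74–0.97. At 30/30, Wald gives 1.00–1.00 and Wilson 0.89–1.00.

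**5. Denominators.** Initiation is divided by those who consent, so n = 24–30 fits. Completion is divided by those who start, so its n is somewhat smaller. If 24 consent and 80% start (an assumption), n is about 19, and Wald coverage at rate 0.82 is 86.8%. Enrollment is divided by everyone screened and found eligible, a number the plan does not give. Assuming 40 to 50, mean coverage over 0.60–0.90 is about 93% and the minimum 86–88%.

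**The case against.** **The plan does not commit to Wald for its results.** The normal-approximation margin stands in the sample-size text, where it projects precision, and the Analytic plan only promises intervals. For associations the plan chooses Fisher's exact and rank tests, so a normal-approximation default cannot be presumed. This stands. A reader might infer that Wald intervals will be reported, but the documents do not say so. What remains is an unnamed method for primary results, with Wald as the only indication.

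**The 80% figure is a worst case.** Coverage moves up and down with n and p. At rate 0.90 it is 80.9% for n = 30 but 93.8% for n = 27. The low values need a true rate near 0.88–0.90, above the earlier estimates. This also stands. A reader might infer that the intervals would typically miss 10–20% of the time, but the average miss rate over the planned range is 8–9%.

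**No decision hangs on the limits.** The plan sets no progression threshold, and the point estimates do not change. This limits the importance of the point without removing it, because the intervals are still meant to inform a larger trial.

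**Wilson assumes independence within groups.** It does, but so does the plan's base analysis and so does Wald. The change neither solves nor worsens clustering.

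**Conclusion.** The point holds as a gap of modest size. The plan promises 95% intervals for its feasibility rates without a method. The one interval it shows, correctly written, covers about 91–92% on average over 0.60–0.90 at n = 24–30, and about 92–93% over the earlier estimates. It reaches about 80% only near rates of 0.88–0.90. The shortfall is mainly on the optimistic side, because most misses are lower limits that are too high.

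The coverage figures assume independent participants and apply to initiation and, roughly, to completion. It would be wrong to carry them over to enrollment, where the denominator is larger and the shortfall smaller. The conclusion does not depend on the missing square root: repairing that alone would leave this point in place.

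**What to change.** In the Analytic plan, add one sentence: 95% intervals for enrollment, initiation and completion will be Wilson score intervals, assuming no class effect as in the base analysis. Clopper-Pearson is an acceptable alternative if a conservative interval is preferred. A continuity correction to Wald is not enough, since its minimum coverage over 0.60–0.90 is still about 87%.

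Under Sample size assessment, replace the margins with expected Wilson limits, [p + z²/(2n) ± z·√(p(1−p)/n + z²/(4n²))] / (1 + z²/n) with z = 1.96. At p = 0.80 and n = 30 this is (0.8640 ± 0.1568)/1.1281, or 0.627–0.905. Evaluated at the planning rates:

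| Rate | n = 30 | n = 27 | n = 24 |
|---|---|---|---|
| 0.60 | 0.423–0.754 | 0.414–0.761 | 0.404–0.769 |
| 0.80 | 0.627–0.905 | 0.617–0.909 | 0.604–0.913 |
| 0.90 | 0.744–0.965 | 0.733–0.967 | 0.720–0.969 |

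For enrollment, state the assumed number screened and eligible and give its limits separately.

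The cost is one sentence and a recalculation that the printed formula requires anyway. No new data are needed. The intervals become asymmetric, so precision is reported as two limits and not as a single margin.

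### The margin-of-error formula omits the square root on p(1−p), so the planned 95% precision for completion and initiation is overstated by about 2 to 2.5 times

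*Combined protocol and SAP*

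**What the plan says.** Section 9, Sample size assessment, names the enrollment and completion rates as primary outcomes and assesses the precision of their estimates. It defines the margin of error as half the width of a two-sided 95% interval and gives this formula: "The margin of error of a 95% confidence interval for a proportion is 1.96*p*(1-p)/(Square-root of n) where n is the estimated sample".

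It then works two examples, each at n = 30, 27 and 24:

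- initiation rate 0.80: "with a margin of error of 0.058, 0.071 and 0.064, respectively"
- completion rate 0.60: "with a margin of error of 0.086, 0.091 and 0.096, respectively"

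The same section says of the planned number: "The sample size was determined based on practical consideration".

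The Analytic plan in Section 9 defines the rates. Enrollment is "defined as the proportion of consented subjects among all screened and eligible patients". Completion means attending at least 6 of the 10 sessions, with the proportion taken "among those who start the intervention". For reporting, it says that "the 95% confidence intervals will be estimated for all outcomes" and names no interval method.

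**The concern.** The standard error of a sample proportion is √(p(1−p)/n). The plan takes the square root of n but not of p(1−p). Since p(1−p) is at most 0.25, leaving off the root always makes the margin too small, by a factor of 1/√(p(1−p)). That factor is 2.04 at p = 0.60 and 2.50 at p = 0.80.

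The primary analysis of this study is descriptive, and its purpose is to inform a larger trial. Interval width is therefore the main measure of what it can deliver on feasibility. A reader who takes the printed margins at face value would expect completion to be estimated about twice as precisely as the design allows.

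Two further points can be seen in the same text. At a fixed rate the margin must shrink as n grows, yet the printed initiation margin is larger at n = 27 (0.071) than at n = 24 (0.064). And although enrollment is named as a primary outcome, the 0.80 example is labelled initiation and no margin is labelled enrollment.

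**Working it through.** **Inputs**, all from Section 9, Sample size assessment: two-sided type I error 0.05 (multiplier 1.96); p = 0.80 (initiation) and p = 0.60 (completion); n = 30, 27 and 24.

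**Step 1. Reproduce the plan's figures from its own formula**, `1.96 × p(1−p) / √n`.

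For p = 0.60 the numerator is 1.96 × 0.24 = 0.4704. For p = 0.80 it is 1.96 × 0.16 = 0.3136. The divisors are √30 = 5.477, √27 = 5.196 and √24 = 4.899.

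| p | n | plan's formula | printed |
|---|---|---|---|
| 0.60 | 30 | 0.0859 | 0.086 |
| 0.60 | 27 | 0.0905 | 0.091 |
| 0.60 | 24 | 0.0960 | 0.096 |
| 0.80 | 30 | 0.0573 | 0.058 |
| 0.80 | 27 | 0.0604 | 0.071 |
| 0.80 | 24 | 0.0640 | 0.064 |

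Four of the six match to rounding. The 0.058 is close (0.0573 rounds to 0.057). The 0.071 does not match.

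**Step 2. Check whether another interval could explain the printed values.** Across the same six settings, the half-widths are 0.139 to 0.183 (Wilson), 0.154 to 0.205 (Clopper-Pearson), 0.120 to 0.165 (90% Wald) and 0.160 to 0.217 (continuity-corrected Wald). None comes near the printed 0.058 to 0.096.

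**Step 3. Restore the square root**, `1.96 × √(p(1−p)/n)`.

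For p = 0.60 the numerator is 1.96 × √0.24 = 0.9602. For p = 0.80 it is 1.96 × √0.16 = 0.7840.

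| p | n | correct margin | printed | correct ÷ printed |
|---|---|---|---|---|
| 0.60 | 30 | 0.175 | 0.086 | 2.04 |
| 0.60 | 27 | 0.185 | 0.091 | 2.03 |
| 0.60 | 24 | 0.196 | 0.096 | 2.04 |
| 0.80 | 30 | 0.143 | 0.058 | 2.47 |
| 0.80 | 27 | 0.151 | 0.071 | 2.13 |
| 0.80 | 24 | 0.160 | 0.064 | 2.50 |

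**Step 4. Put the difference on the scale of the rate.** For completion at p = 0.60 and n = 24, the printed margin implies 0.60 ± 0.096, or 0.504 to 0.696. The correct interval is 0.60 ± 0.196, or 0.404 to 0.796. The plan quotes 0.57 to 0.82 from earlier work for the enrollment and completion rates. The correct interval covers (0.796 − 0.57)/(0.82 − 0.57) = 0.904 of that range. The printed one covers (0.696 − 0.57)/0.25 = 0.504.

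**Step 5. Sample size at which the printed margins would be true**, `n = 1.96² × p(1−p) / m²`, where m is the printed margin.

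- p = 0.60, m = 0.086: 3.8416 × 0.24 / 0.007396 = 124.7, so 125
- p = 0.80, m = 0.058: 3.8416 × 0.16 / 0.003364 = 182.7, so 183

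The plan has 24 to 30.

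**Step 6. Sensitivity to the denominator.** Completion is taken among those who start. Assume that 24 to 30 people consent and that 80% start, as in the plan's own illustration. Then about 19 to 24 start, and the margin at p = 0.60 is 1.96 × √(0.24/24) = 0.196 to 1.96 × √(0.24/19) = 0.220.

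**The case against.** The strongest case on the other side is about consequence, not arithmetic. N was set on practical grounds, the primary analysis is descriptive, and no progression rule uses a margin. The COVID-19 text shows that the first cohort was already under way. Correcting the formula changes no participant number, procedure or planned analysis. All of this stands and limits the practical effect. It does not make the stated precision true.

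Second, the 2.5-fold figure belongs to initiation, which is not named as primary. For completion, the one primary rate with a printed margin, the factor is about 2.0. That is right and should be kept in view.

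Third, the replacement margins take 24 to 30 as the denominator and assume no clustering, while completion is defined among starters and the plan itself allows that group membership may affect attendance. This also stands. With fewer starters the margins are wider still (Step 6), as they would be with positive within-group correlation, so the objection does not rescue the printed values.

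Fourth, the overlap with 0.57 to 0.82 is only an illustration. The plan gives that range for enrollment and completion together, and overlap is not one of its criteria. The finding does not depend on it.

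Finally, nothing says that the faulty formula will be used to report results, and the plan says the sample size analyses were done in R. That is fair. The charge is that the planned precision is misstated, not that the final intervals will be wrong.

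**Conclusion.** The concern holds. The formula is wrong as written, five of the six printed margins follow it exactly or nearly, and the sixth (0.071) follows neither it nor any of the standard intervals tried. All six are too small: by a factor of 2.03 to 2.04 for completion at 0.60, and 2.13 to 2.50 for initiation at 0.80. No other part of the document corrects this.

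The corrected values rest on the Wald interval, the plan's own n of 24 to 30 as the denominator, and independence between participants. The conclusion that the printed margins are far too small does not depend on choosing Wald, since Wilson and exact half-widths are of similar size to the corrected ones. The error did not determine N. It should still be corrected, because it misstates the precision of a primary outcome in a study whose main output is estimates.

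**What to change.** - Replace the formula with `1.96 × √(p(1−p)/n)`.
- Restate the margins for n = 30, 27 and 24 as 0.143, 0.151 and 0.160 at p = 0.80, and 0.175, 0.185 and 0.196 at p = 0.60.
- Add a margin labelled as enrollment, since that is a primary outcome.
- Give the expected denominator beside each margin: screened and eligible patients for enrollment, consented subjects for initiation, starters for completion. If fewer than 24 to 30 are expected to start, recompute the completion margins at that number. Say that the margins assume no clustering by group.
- Optionally, name the Wilson or exact method for the reported rates. At n = 24 to 30 and true rates of 0.80 and 0.90, the exact coverage of the nominal 95% Wald interval is 0.81 to 0.95, against 0.95 to 0.97 for Wilson.

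The cost is a text correction. Participant numbers, procedures and decision rules stay as they are. The stated precision becomes about half as good for completion and, in places, less than half as good for initiation, which is what the design delivers.
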